2.8 STUDY ORGANIZATION

2.8.1 Electronic Data Capture (EDC)

MedNet Solutions Incorporated is a privately-held company that specializes in Web-based clinical database and data management technology. MedNet's responsibility is to partner with BIOTRONIK in the development, implementation, and on-going support of a system for an eClinical Solution including EDC of clinical trial data for the CELESTIAL post-approval registry. MedNet will configure a web-based eClinical system to meet the specific goals and needs of BIOTRONIK for the CELESTIAL registry. MedNet will host the Oracle database utilized for the EDC system. This system is 21 CFR Part 11 compliant and will be the conduit for the electronic case report form (eCRF) data entry, data validation, and access to real-time configured functions, tools, and reports for BIOTRONIK, specified investigational sites, and any other parties authorized by BIOTRONIK.

CELESTIAL REGISTRY PROTOCOL

3. PROTOCOL REQUIREMENTS

3.1 PATIENT POPULATION

This post approval registry will include a minimum of 2500 patients from up to 100 centers. The collection of data will continue for five years for each enrolled subject.

The investigator is responsible for screening all potential patients and selecting those who are appropriate for registry inclusion. The patients selected for participation should be from the investigator's general patient population according to the inclusion and exclusion criteria described below. Patients declining participation will be documented on a screen failure log describing the primary reason.

3.1.1 Indications

Corox BP LV Lead

The Corox OTW BP, Corox OTW-S BP, and Corox OTW-L BP left ventricular pacing leads are bipolar steroid-eluting leads, intended for permanent implantation in the left ventricle via the coronary veins to provide pacing and/or sensing when used in conjunction with a compatible IS-1 pulse generator.

In this post-approval registry, any legally-marketed BIOTRONIK CRT device may be used (e.g. CRT-D: Lumax HF-T and any future CRT-D; CRT-P: Stratos LV and any future CRT-P).

3.1.2 Contraindications

Corox BP LV Lead

The use of the Corox BP LV leads is contraindicated under the following circumstances:

- Coronary sinus anomalies
- Tissue in the coronary sinus area that has been damaged by an infarction
- Any anomalies of the venous system that preclude transvenous implantation of the lead
- Patient cannot tolerate a single systemic dose of up to 1.0 mg of dexamethasone acetate (DXA)

3.1.3 Inclusion Criteria

To support the objectives of this post-approval registry, patients are required to meet the following inclusion criteria prior to enrollment:

- Successfully implanted BIOTRONIK CRT system, including a Corox BP LV lead, from 7-180 days prior to enrollment.
- Able to understand the nature of the registry and give informed consent

CELESTIAL REGISTRY PROTOCOL

- Available for follow-up visits on a regular basis at the investigational site
- Age greater than or equal to 18 years

3.1.4 Exclusion Criteria

To support the objectives of this registry, the exclusion criteria at the time of patient enrollment include:

- Enrolled in any IDE clinical study
- Planned cardiac surgical procedures or interventional measures within the next 6 months
- Expected to receive a heart transplant within 1 year
- Life expectancy less than 1 year
- Presence of another life-threatening, underlying illness separate from their cardiac disorder
- Pregnancy
- Inability to provide date of implant, devices implanted, age, gender, and whether the patient experienced any protocol-defined adverse events since implant

3.2 POST APPROVAL REGISTRY DESIGN

3.2.1 Procedure

This is a prospective registry involving a minimum of 2500 subjects from up to 100 centers. Subjects will be enrolled 7-180 days after successful implantation of a BIOTRONIK CRT device utilizing a Corox BP LV lead. At enrollment, each registry patient should have CRT programmed "ON". Additionally, BIOTRONIK Home Monitoring should be activated in all subjects. Standard Home Monitoring reports will be available to investigators. Home monitoring data can be utilized to assist in triage and diagnosis of LV lead-related adverse events.

3.2.2 Study Visits

The specific visits that are part of this registry are provided in the following bullets, and the procedures are described in more detail in the following sections:

- Screening Visit
- Enrollment
- Routine and unscheduled follow-ups through 5 years post-implant (every subsequent follow up that is scheduled according to each institution's standard of care)

CELESTIAL REGISTRY PROTOCOL

3.2.3 Screening Visit

Prior to enrollment, the patient's background and history must be reviewed in order to ensure they are an appropriate candidate for the registry. In addition, all patients must satisfy the inclusion and exclusion criteria prior to enrollment, including having an implanted BIOTRONIK CRT system utilizing a Corox BP LV lead. After the patient has passed this screening process, informed consent must be obtained from the patient prior to initiating any registry-related procedures.

The following are required at this visit:

- Ensure registry candidacy by answering inclusion and exclusion criteria
- Administer Informed consent

3.2.4 Enrollment Visit (within 30 days of screening visit)

After Informed Consent has been obtained and the patient has been determined to be eligible for the registry, data is collected in the Enrollment Visit. Typically the Screening Visit and the Enrollment Visit happen concurrently.

The following are required at the Enrollment Visit:

- Collect retrospective implant information from medical chart review
 - Date of implant
 - Implant approach/method, and venous access
 - Implant location of pulse generator and implanted leads
 - Implant procedure durations, if available
- Collect patient demographics (gender, height, weight, etc.)
- Medical history of patient
 - Bradycardia or ICD indication with Heart Failure
 - NYHA classification
 - LVEF %, if available; date and method obtained
- Collect information on implanted system (pulse generator and leads manufacturer/model, serial numbers, etc.)
- Record electrical parameters of the implanted leads
- Record any cardiac related adverse event between implant and the enrollment visit

Programming parameters should be set to best suit the needs of the patient. If adequate system function, including effective CRT, cannot be obtained, the patient should not be enrolled in this registry.

CELESTIAL REGISTRY PROTOCOL

3.2.5 Routine and Unscheduled Follow-Ups

Patients enrolled in the CELESTIAL post approval registry can be implanted with either a CRT Pacemaker (CRT-P) or a CRT Defibrillator (CRT-D). Follow-up schedules for these devices vary by practice, but typically occur every 3-4 months for a CRT-D and every 6 months for a CRT-P. Therefore patients will be seen for routine follow-up visits per their institutional standard of care, but not to exceed every 6 months. All scheduled follow up windows are ± 1 month.

Any time a patient is seen outside of a required follow-up window according to each site's pre-determined specific follow-up scheduling practice, that visit is considered an unscheduled follow-up. Each site Principal Investigator (PI) and Clinical Research Coordinator (CRC) will be trained to identify and schedule follow-ups to meet this expectation. Additionally, the EDC will provide assistance in identifying properly scheduled follow-ups according to this protocol by assisting in the selection of the proper electronic Case Report Form (eCRF).

The following are required at each follow-up visit:

- Interrogate programmed parameters
- Determine lead electrical parameters
- Evaluate device diagnostics and programmed parameters to ensure CRT is programmed "ON" and the device is correctly providing CRT therapy
- Record % of CRT pacing
- Determine if there are any cardiac-related Adverse Events. If there are, complete the Adverse Event eCRF
- Complete all appropriate eCRF's

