2.1 STUDY ENDPOINTS

This clinical investigation includes the assessments of two primary safety endpoints related to the Corox BP LV leads, and several secondary endpoints that include an evaluation of the long-term delivery of biventricular pacing by BIOTRONIK CRT study devices. The hypotheses associated with the primary safety endpoints are presented below.

2.2 PRIMARY ENDPOINT 1: SAFETY OF COROX BP LV LEADS PACING – OVERALL COMPLICATION-FREE RATE

The purpose of primary endpoint 1 is to evaluate the overall incidence of serious adverse events that require additional invasive intervention to resolve, related to the Corox BP LV leads implanted with either BIOTRONIK CRT-P or CRT-D devices.

Primary safety endpoint 1 is constructed to capture all LV lead-related serious adverse events, not limited to fractures and insulation failures, but excluding those well documented adverse events that do not reflect a LV lead failure.

The following serious adverse events have been collected and reported by each LV lead manufacturer in their respective Summary of Safety and Effectiveness Data Reports (P050045, P050023, P030035, P010031, P010015, and P010012). While these SAEs will not be counted toward primary endpoint, they will be collected and analyzed as pre-specified secondary endpoints.

Table 4: Adverse Event Exclusions

Adverse Event Exclusions	Estimates of rates from prior studies
Inability to place LV Lead	10 - 14%
Lead dislodgements up to 180 days post implant procedure	1.9 - 9%
High LV pacing threshold, intermittent LV capture, no capture of LV lead	3.6 - 5.6%
Diaphragmatic/pectoral stimulation	0.2 - 2.9%
Infection	1.6 - 2.3%
Atrial lead, ICD lead, or generator adverse events requiring additional interventions	1.6 - 36.8%
Non LV lead related hospitalizations	27.4 - 48.9%
Non LV lead related death	6.2 - 18.9%
Implant procedure related complications such as CS dissection, CS perforation, pneumothorax, arrhythmias, cardiac tamponade, hematoma	1.5 - 13.3%
LV lead related thrombosis	<0.5%
Implant damage to LV lead (e.g. accidental cut to lead body during pocket revision, device replacement, etc.)	0.2 - 0.9%
Twiddler's syndrome	0.2%

Assuming that the expected Corox BP LV lead-related serious adverse event rate (proportion of subjects with at least one SAE), excluding the above, is 7.5% or less, then the primary safety endpoint will be evaluated in the following testable hypothesis in a noninferiority format.

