2.4 SECONDARY ENDPOINTS

1. Successful biventricular pacing in a BIOTRONIK CRT device at scheduled CELESTIAL registry follow-up visits through 5 years post-enrollment
2. Serious adverse event rates for SAEs excluded from primary safety endpoint (listed in Table 4) through 5 years post-enrollment.
3. Pacing threshold, sensing and impedance measurements for the Corox BP leads at scheduled CELESTIAL registry through 5 years post-enrollment
4. Individual electrical parameters of the Corox OTW BP LV lead, the Corox OTW-S BP LV lead, and the Corox OTW-L BP LV lead.
5. Overall incidence of serious adverse events that meet the primary endpoint 1 criteria will be evaluated separately for each Corox BP lead model.
6. Incidence of individual types of serious adverse events contributing to primary endpoint 2 will be evaluated separately for each Corox BP lead model.

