4. STUDY DOCUMENTATION AND DATA COLLECTION

4.1 ELECTRONIC CASE REPORT FORMS (eCRFs)

Original data will be collected from each investigational site and recorded into a secure Electronic Data Capture (EDC) application hosted by MedNet Solutions, Minneapolis, Minnesota, and audited and monitored by BIOTRONIK.

Information from electronically delivered source data (e.g. programmers) will be captured and stored in a validated environment until the end of the study.

The investigator will be required to use his/her electronic signature to verify the content of the data reported in the eCRFs.

Patient follow-up is required for all subjects enrolled in this clinical registry. The follow-up visit date is based on the Corox BP LV lead implant date, and are to be used for:

CELESTIAL REGISTRY PROTOCOL

- Screening Visit
- Enrollment (7-180 days after Corox BP LV lead implant or lead revision)
- Medical History and Implant (at enrollment)
- Routine follow-ups (every 3-4 months for a CRT-D and every 6 months for a CRT-P, \pm 1 month)
- Unscheduled cardiac related physician or hospital visits
- Final 5 Year follow-up (\pm 1 month)
- All cause Adverse Events
- Study Exit
- Patient Non-Compliance

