7.6 ADVERSE EVENTS

The investigator will be required to assess the association of each reported adverse event to the implant procedure, implanted system including the generator, any lead, or the Corox BP LV lead. For each of these relationships, the investigators will indicate whether the Adverse Event is not related, related, possibly related, or unknown.

All Adverse Events will be adjudicated by the Clinical Events Committee (see Section 7.7 Clinical Events Committee). The Clinical Events Committee (CEC) will have the responsibility to adjudicate all Adverse Events into one of the following three final classifications: related, not related, or unknown.

CELESTIAL REGISTRY PROTOCOL

In evaluation of the two primary safety endpoints, the estimates of SAE rates will be based on the number of patients with at least one related SAE as a proportion of total patients with no SAEs, related SAEs, or unrelated SAEs. Patients with a final adjudicated relatedness SAE classification of unknown will not have that individual unknown event contribute to or be included in the evaluation of primary safety endpoint 1 (overall complication-free rate). Patients with an adjudicated relatedness SAE classification of unknown for a specific type of individual SAE will not have that individual unknown event contribute to or be included in the evaluation of that type of SAE in primary safety endpoint 2. However, for purposes of Kaplan-Meier actuarial analyses, described in Section 2.7.1 Trend Analyses and Section 2.7.2 Missing Data, all SAE data on enrolled patients will be included, with follow-up time censored at the time of withdrawal or last completed follow-up visit.

For the purposes of this registry, an adverse event is considered to be implant related if any one of the following occurred:

- Coronary sinus dissection
- Coronary sinus perforation
- Pneumothorax
- Arrhythmias
- Cardiac Perforation with or without tamponade
- Non-healing pocket dehiscence requiring intervention
- Hematoma
- Other event requiring surgical intervention

Additionally, for purposes of this registry, an adverse event is considered to have occurred at any point if both of the following conditions are met:

Condition One (definitions can be found in Appendix A: Definition of Terms)

- Infection
- Cardiac perforation with or without tamponade
- Lead dislodgment
- High pacing threshold, intermittent capture, no lead capture
- Diaphragmatic/pectoral stimulation

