- Lead impedance out of range, high impedance
- Lead impedance out of range, low impedance
- Lead related thrombosis
- Implant damage to lead (e.g. accidental cut to lead body during pocket revision, device replacement, etc.)
- Premature battery depletion
- Suspected lead failure
- Suspected generator failure
- Twiddler's Syndrome
- Lead undersensing or loss of sensing
- Skin erosion

Condition Two:

- Lead pacing polarity or pacing mode reprogrammed due to suspected lead failure
- Lead surgically repositioned
- Lead surgically explanted
- Lead surgically replaced
- Lead surgically abandoned
- Lead abandoned and pacing disabled
- Lead use continued based on medical judgment despite a known clinical performance issue
- Other lead related surgery performed

Note: If Condition One is corrected by reprogramming the pulse generator or lead (other than changing the polarity or pacing mode) and no other invasive action was taken, then the event will not be considered an adverse event and should not be reported. Similarly, programming changes in pacing polarity/vector or pacing mode that are not due to a suspected lead failure will likewise not be considered an adverse event and should not be reported. For example, electrical reprogramming of the pacing polarity to eliminate diaphragmatic stimulation will not be considered an adverse event.

The adverse events that the IRB considers reportable are dependent on the particular IRB. The protocol-defined Adverse Events not related to the Corox BP LV lead are detailed in Table 4. To avoid underreporting, BIOTRONIK recommends that, at a minimum, the investigational site reports the adverse events detailed above that occur during the CELESTIAL post approval study to BIOTRONIK and their IRB.

The investigational site should report the Adverse Event on the Adverse Event eCRF. Additionally, registry sites may report adverse events through MedWatch, FDA's adverse event reporting tool for market-released devices. As defined in BIOTRONIK's internal procedures, these adverse events may be reported by BIOTRONIK through manufacturer's MedWatch reports.

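### Adverse event collection rules conflict with secondary endpoint 2, so the non-LV-lead hospitalization and generator rates may be under-counted or collected differently across sites

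*Protocol*

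**What the plan says.** **The endpoint.** Protocol 2.4 sets secondary endpoint 2 as "Serious adverse event rates for SAEs excluded from primary safety endpoint (listed in Table 4) through 5 years post-enrollment". The text above Table 4 commits to collecting and analyzing these events. SAP 5.3.2 asks for event rates, a Kaplan-Meier graph and a 5-year freedom-from-event estimate with standard error and 95% interval, in all enrolled subjects. Two of the Table 4 rows are "Non LV lead related hospitalizations" and "Atrial lead, ICD lead, or generator adverse events requiring additional interventions".

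**The visit checklists.** At enrollment (3.2.4) sites are to "Record any cardiac related adverse event between implant and the enrollment visit". At each follow-up (3.2.5) they are to "Determine if there are any cardiac-related Adverse Events", and a positive answer triggers the Adverse Event eCRF.

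**The form list.** Protocol 4.1 includes "All cause Adverse Events", and 2.5 names all-cause events among the additional data to be collected.

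**The definition.** Protocol 7.6 gives a list of implant-related events, any one of which suffices. For all other events it says "an adverse event is considered to have occurred at any point if both of the following conditions are met". Condition One lists findings, among them suspected generator failure and premature battery depletion. Condition Two lists responses. Each concerns a lead, ending with "Other lead related surgery performed".

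**The concern.** The endpoint and the form list point to all-cause collection. The visit checklists and the operational definition are narrower. A site that works from the checklist and 7.6 has no prompt for a non-cardiac admission, and a generator replaced without any lead action does not meet the definition. A site that works from 4.1 would report both.

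An event that is never reported leaves the patient event-free in the Kaplan-Meier estimate. The rate is then biased downward, and its confidence interval gives no sign of it. The result may be read beside the prior-study ranges in Table 4, where a low figure would look reassuring. If sites differ in which rule they follow, the pooled rate also mixes two ascertainment rules.

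**Working it through.** The plan states no sample size, power or expected rate for secondary endpoint 2, so there is no figure to reproduce. The check is a reconciliation of each Table 4 row with the rules that would capture it.

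| Table 4 row | Route through the checklists and 7.6 | Other route | What remains open |
|---|---|---|---|
| Non-LV-lead hospitalization | On neither 7.6 list; prompted at visits only if cardiac | All-cause eCRF; form for unscheduled cardiac physician or hospital visits (4.1) | Mainly non-cardiac admissions; also, nothing says a cardiac visit form becomes an adjudicated SAE |
| Generator events needing intervention | Condition One met; no Condition Two item fits a generator-only action | All-cause eCRF; a surgical catch-all, but on the implant-related list | Generator-only interventions |
| Atrial or ICD lead events | Condition One items with lead actions in Condition Two | All-cause eCRF | Little |
| Dislodgement, threshold or capture problems, stimulation, thrombosis, lead damage, Twiddler's syndrome | Condition One items with lead actions in Condition Two | All-cause eCRF | Little |
| Infection | Condition One, but still needs a lead action | All-cause eCRF | Infections handled without a lead action |
| Implant procedure complications | Any-one list, including hematoma and pneumothorax | All-cause eCRF | Little |
| Non-LV-lead death | Not needed | Study Exit eCRF (7.8) | None |
| Inability to place the lead | Enrollment follows a successful implant (3.1.3) | Not applicable | Does not turn on these rules |

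Two further passages show that 7.6 can act as a filter. Its Note says that some findings corrected by reprogramming alone are not to be reported. SAP 2.4 counts elevated thresholds in the FDA-requested analysis whether or not they met the protocol's adverse event definition, which treats that definition as a gate.

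**Illustration of scale.** The fraction of events captured, c, is an assumption; the documents give none. Observed rate = true rate × c, with the Table 4 prior-study ranges standing in for the true rate.

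| c | Hospitalization (27.4–48.9%) | Atrial lead, ICD lead or generator (1.6–36.8%) |
|---|---|---|
| 0.25 | 6.85–12.23% | 0.4–9.2% |
| 0.50 | 13.70–24.45% | 0.8–18.4% |
| 0.75 | 20.55–36.68% | 1.2–27.6% |
| 1.00 | 27.4–48.9% | 1.6–36.8% |

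For the second row, c applies to the row as a whole. Only its generator share is exposed, and the documents do not give that share.

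For comparison, take 2500 patients and the exact binomial 95% interval. A rate of 27.4% has the interval 25.66–29.19%, a half-width of (29.19 − 25.66)/2 ≈ 1.8 points. A rate of 48.9% has the interval 46.90–50.86%, a half-width of about 2.0 points. Even at c = 0.75 the hospitalization rate would fall by 27.4 − 20.55 = 6.85 points or more, well outside the interval. At c = 1.00 there is no loss.

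**The case against.** The strongest reply is that the protocol does provide for all-cause collection. The 3.2.5 checklist also tells sites to complete every appropriate eCRF, and 4.1 names an all-cause form. Appendix A defines an adverse event broadly. Section 7.6 calls its list a minimum for reporting and describes the Table 4 events as protocol-defined. An exclusion criterion in 3.1.4 removes patients who cannot say whether such events have occurred since implant. Cardiac admissions have a visit form of their own. Investigators must judge relatedness to the generator, and SAP 3.2 uses a system revision date, so revisions are evidently recorded. Secondary endpoint 2 carries no hypothesis, and Table 4 events do not enter either primary endpoint.

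Most of this stands, and it rules out four stronger readings that a reader might infer:

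- *The hospitalization rate will be close to zero.* This assumes that every site applies 7.6 as a complete filter and ignores the all-cause form.
- *Generator events are lost.* They are Condition One items, and the all-cause form would take them. What is missing is a matching Condition Two action.
- *All Table 4 rates will be falsely low.* The table above shows that the other rows largely have a route.
- *The number missed can be computed.* 2500 × 0.274 = 685 and 2500 × 0.489 ≈ 1223, but the Table 4 ranges come from prior studies, have no stated follow-up time and are not forecasts for this registry. These products show neither what will occur nor what will go unreported.

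The reply does not remove the conflict. An all-cause form does not cancel a cardiac-only prompt or a definition that requires both conditions. Sending a late generator replacement through the surgical item on the implant-related list would place it under a different Table 4 row.

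**Conclusion.** The concern holds as an internal inconsistency. It puts at risk the non-LV-lead hospitalization row and the generator part of the atrial lead, ICD lead or generator row. The direction of any within-site error is downward. Its size is unknown, ranging from nothing under full all-cause reporting to a shortfall well beyond sampling error if a quarter or more of hospitalizations went unreported (an assumed fraction). The conclusion assumes that at least some sites will work from the visit checklists and 7.6 rather than from the form list in 4.1. Confidence is moderate. The primary endpoints are not affected by this point.

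**What to change.** 1. Delete the cardiac restriction from the adverse event bullets in 3.2.4 and 3.2.5, so that they agree with the all-cause eCRF in 4.1.
2. Add a generator action (explanted, replaced or revised) to the Condition Two reporting list in 7.6.
3. State in 7.6 that each Table 4 row is reportable in its own right, and name the form that captures it.
4. If non-LV-lead hospitalizations will not be collected systematically, report no rate for that row under secondary endpoint 2 and SAP 5.3.2. Alternatively, label the rate as incompletely ascertained and not comparable with the Table 4 range.

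The first three are changes to protocol wording and eCRF guidance. Their cost is more site reporting and more adjudication, because 7.6 and 7.7 send all adverse events to the Clinical Events Committee. The fourth avoids that load but gives up part of a pre-specified endpoint in an FDA-required registry, so it is more than an edit.
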